1 STUDY OBJECTIVES

1.1 Primary Objective

The purpose of this study is to evaluate the safety, feasibility and outcome of administering three different statins at submaximal and maximal dose on eCD and dCD. We hypothesize that a pre-operative statin regimen is protective against eCD (12-25h post-CEA) and dCD (30d), and early (365d) mortality. In addition, maximal doses may be essential in achieving optimal neuroprotection against eCD and dCD, with statins that pass the blood-brain barrier achieving similar effects at lower doses due to enhanced entry into the brain. In order to test this, our primary objectives will be:

- 1) Determine whether patients on a pre-existing sub-maximal dose of one of three most commonly prescribed statins (simvastatin <40mg, atorvastatin <80mg, rosuvastatin <20mg) experience a higher incidence of eCD and dCD than those randomized to 218 doses of pre-operative statin supplementation to the maximal FDA approved dose (simvastatin 40 mg, atorvastatin 80 mg, rosuvastatin 20 mg).
- 2) Determine whether approximately 2-18 doses of maximal statin supplementation is sufficient by comparing whether patients randomized to receiving statin supplementation each individually experience a higher incidence of eCD and dCD than those patients on a pre-existing maximal dose of the three most common statins, and whether statins that pass the blood-brain barrier better correlate with reduced eCD and dCD.
- 3) Determine whether patients on no pre-existing statin regimen exhibit less eCD and dCD when randomized to 2-18 doses of pre-operative maximal dose of atorvastatin (80mg) compared to lower dose of atorvastatin (10mg).
- 4) Determine a dose-response relationship to these 3 statins by determining whether all patients at the time of surgery have less eCD and dCD if they are on: 1) simvastatin 40mg rather than on <40mg; 2) atorvastatin 80mg rather than on <80mg; and 3) rosuvastatin 20mg rather than on <20mg.

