The participant's statin therapy after their CEA will be determined by their attending or primary care doctors and not the study physicians. The study team will inform the participant and their attending doctors. Their primary care doctor will receive a letter informing them of their patient's study participation (see Appendix V PMD letter).

The study will evaluate if the changes in statin regimen prior to CEA are neuroprotective against eCD (12-25 hours post-CEA) and dCD (30 +/- 5 days post-CEA or day of their post-CEA clinical visit) with neuropsychometric tests. The neuropsychometric tests are designed to demonstrate general neuropsychological performance and not to be diagnostic of specific neuropsychiatric disorders. The average amount of time to complete the neuropsychometric battery is 30-45 minutes. Individual subject participation will conclude Day 365 +/- 30 days post-CEA to assess morbidity and mortality (Figure 7). Consequently, the individual subject participation will be one year post CEA and the overall study completion timeline will be five years of enrollment years plus one year follow up for the last participant enrolled to complete follow up.

Figure 7: Study Participation Timeline

** follow-up calls before CEA will be conducted only if not preceded by CEA

We have defined our primary outcome on Z-scores based on the mean and standard deviation of cognitive testing change in scores of a surgical reference group before and after surgery (1225h and approximately 30 days post-op). Consequently anyone with: (a) $\geq 2SD$ worse than reference group in two or more cognitive domains or (b) $\geq 1.5SD$ worse than the reference group in all cognitive domains tested will be considered a primary outcome.

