5 STUDY INTERVENTIONS

5.1 Interventions, Administration, and Duration

The study assigned statin dosing will be taken daily for no fewer than 2 and no greater than 18 doses prior to the participant's CEA. If the encounter and enrollment happen prior to the 18 day timepoint and the patient cannot return to the study site prior to their CEA, then the subject will be given the study drug and begin taking it no greater than 18 days prior to their CEA. We will strive to enroll the subjects as early as possible so that they may receive as many doses (up to 18 doses) prior to CEA. The date of drug start will be noted in the Medication Compliance form (diary) and the eCRF upon enrollment. The safety follow-up phone calls will begin based on when the study drug is scheduled to start or upon enrollment for Arm 1. All of the participants in each arm will be provided with instructions in the Study Medication Compliance form where they will note each dose taken or the reason(s) for missing a dose. This includes logging in their current statin use for the observational/ maximal dose group (Arm 1) and the sub-maximal dose group (Arm 2). This form will be collected when the subject returns to the medical center for their CEA. The treatment arms are as follows:

ARM 1: Subjects already on **maximal daily doses** will continue to take their daily statin during the dosing period prior to CEA (atorvastatin 80 mg, simvastatin 40 mg with/without amlodipine or simvastatin 20 mg plus amlodipine, or rosuvastatin 20 mg). No additional drug will be dispensed to this group.

ARM 2: Subjects on **sub-maximal daily doses** (atorvastatin <80 mg or simvastatin <40 mg without amlodipine and <20 mg on amlodipine or rosuvastatin <20 mg) will continue to take their daily statin during the dosing period prior to CEA PLUS they will be given the corresponding study drug bottles of:

- **Atorvastatin vs Placebo (each active study capsule = 10 mg)**

- 126 capsule count bottle
 - Coordinator will write on the label how many capsules the participants need to take when they take their statin drug each day (example: If subject is currently on 10 mg of atorvastatin, then they will need to add 7 capsules/day to potentially reach 80 mg of active drug.)

- **Simvastatin vs Placebo (each study capsule = 5 mg)**

- 126 capsule count bottle
 - Coordinator will write on the label how many capsules they need to take when they take their statin drug each day (example: If subject is

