Investigators will not be involved in preparation or delivery of drug to maintain the blind. BRINM has prepared blinded and randomized drug supplies for several randomized trials. It will provide all pharmacy support for the study, including preparation of the randomization schedule, placebo and active statin drug supplies, monitoring of procedures for shipping drug to multiple sites, and documentation of drug handling and disposal of remaining study drug at its site.

Inventory will be monitored by BRINM to make sure that we maintain at least 3 bottles for each randomization option for any potential enrollment of subjects in ARM 2 and ARM 3. This will allow adequate inventory at each site for any potential randomization. Consequently, we will strive to maintain 24 bottles of study drug at each site [ARM 2 requires 6 study bottles for the atorvastatin group (3 placebo + 3 active drug for maximization); 6 study bottles for the simvastatin group (3 placebo + 3 active drug for maximization), and 6 study bottles for the rosuvastatin group (3 placebo + 3 active drug for maximization) while ARM 3 will require 3 bottles of 10 mg atorvastatin and 3 bottles of 80 mg atorvastatin.] Upon randomization of each subject, the study database will automatically send an email to BRINM to inform them of the bottle number used and the study option that needs to be replenished.

The study drug will be requested from the site's research pharmacy with a doctor's order, copy of 1st and signature page of the consent form, copy of the randomization page from the study website, site approved cover fax form, and in accordance with regulatory and pharmacy procedures. Study treatment is to be dispensed only to subjects enrolled in this study. Study treatment must be dispensed only by a pharmacist or appropriately qualified staff. Once study treatment is dispensed to a subject, it cannot be used for another. Study treatment bottles are only for the dosing period prior to CEA. None of the remaining capsules from one subject can be used for another subject.

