5.3 Concomitant Interventions

A concomitant therapy is any drug or substance administered between time of informed consent to enroll and completion of assessments at Day 365 +/- 30 days post-CEA. The use of concomitant therapies or procedures must be recorded on the subject's Concomitant Medications and Adverse Events eCRFs, according to instructions for completion and data entry. All AEs following the administration of these therapies or procedures must be documented on the appropriate worksheet/eCRF, regardless of relatedness.

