This is a phase III study for asymptomatic patients with carotid artery stenosis designed to assess if maximizing statin doses for approximately two weeks (12-18 days) prior to carotid endarterectomy (CEA) is neuroprotective. Patients who are already on the maximal statin dose of either atorvastatin (80 mg), simvastatin (40 mg) or rosuvastatin (20 mg) will remain on their current doses and will be part of our observational arm. The patients that are currently on sub-maximal daily doses of the previously mentioned statins will be randomized to either 1) their current dose plus placebo or 2) their current dose plus the necessary milligrams needed to bring them to the FDA approved maximal dose per day for their corresponding statin. Those patients who are statin naïve, 30 days prior to enrollment, will be randomized to daily doses of either 1) 10 mg of atorvastatin or 2) 80 mg of atorvastatin.

We will stay in contact with Mr./Mrs. _____ via phone calls prior to the CEA to assure study drug compliance and safety. We will also assess him/her prior to the CEA, 12-25 hours post-CEA, and during their post-operative clinical visit (approximately at 30 days post-CEA) for early cognitive dysfunction (eCD). The final follow-up phone call will be one year after their CEA procedure.

We have attached a copy of your patient's study consent form. We ask that you not alter your patient's assigned statin dose unless it is clinically necessary. If you do change their dose prior to their CEA, please let us know. After their CEA, Mr./Mrs. _____ will be prescribed statins as per the standard of care for post-CEA patients by their treating physician and will not receive any further study drugs.

If you have questions, please do not hesitate to contact our Study Clinical Coordinator, [name of coordinator] at [contact number] or one of us.

Sincerely yours,

[Contact Information for Principal Investigator at Site]

• Appendix VI: Delegation of Authority Log

STANCE TRIAL
SITE PERSONNEL SIGNATURES & DELEGATED RESPONSIBILITIES LOG

Study Site: _____

NAME (PRINT OR TYPE)	SIGNATURE	INITIALS	STUDY ROLE (i.e. Site PI, Study physician, sub-investigators, Study Coordinator, Research Pharmacy, etc)	DELEGATED RESPONSIBILITIES* (list all that apply A-I)	DATES (Involved in STUDY) (mm/dd/yyyy)	PI Initials/Date (mm/dd/yyyy)
					Start: _____ Stop: _____	
					Start: _____ Stop: _____	
					Start: _____ Stop: _____	
					Start: _____ Stop: _____	
					Start: _____ Stop: _____	

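### Post-operative statin dose is uncontrolled and likely to differ between Arm 1 and supplemented Arm 2, so the Day 30 (dCD) part of Objective 2 is confounded

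*Combined protocol and SAP*

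**What the plan says.** **Study drug is pre-operative only.** Section 5.2: "Study treatment bottles are only for the dosing period prior to CEA". Section 5.4 has the bottles collected when the patient is admitted for CEA.

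**Afterwards the treating doctors decide.** Section 3 on all participants: "statin therapy after their CEA will be determined by their attending or primary care doctors and not the study physicians". The letter to the primary doctor (Appendix V) describes later treatment this way: "prescribed statins as per the standard of care for post-CEA patients by their treating physician and will not receive any further study drugs".

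**Supplementation is an add-on.** Under Section 5.1, Arm 2 patients keep taking their own sub-maximal statin and add study capsules. Arm 1 receives no study drug: these patients "will continue to take their daily statin during the dosing period prior to CEA (atorvastatin 80 mg, simvastatin 40 mg with/without amlodipine", among other listed regimens. That sentence covers only the period before surgery.

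**Objective 2 (Section 1.1)** opens with the sufficiency question: "Determine whether approximately 2-18 doses of maximal statin supplementation is sufficient by comparing whether patients randomized to receiving statin supplementation". The yardstick is Arm 1. The test is whether the supplemented patients "each individually experience a higher incidence of eCD and dCD than those patients on a pre-existing maximal dose", so both outcomes count. **Objective 4** is a dose-response question, "determining whether all patients at the time of surgery have less eCD and dCD if they are on" the maximal dose of each statin and not on less.

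**Outcomes.** dCD is tested at Day 30 +/- 5 or at the post-operative clinic visit (Section 3). Section 9.2 makes eCD the response in the primary regression for every aim and gives dCD a separate analysis.

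**Data.** Section 5.3 has concomitant therapy recorded, defined as "any drug or substance administered between time of informed consent to enroll and completion of assessments at Day 365". Section 6.2.5 repeats the medication review at the Day 30 visit.

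**The concern.** When the capsules stop, an Arm 2 patient is left with a sub-maximal prescription of their own. Nothing is withdrawn from an Arm 1 patient. Allocation in Arm 2 is blinded (Sections 5.2 and 9.2.1), so a doctor would not normally know which patients had been raised. Unless prescriptions are changed, the two Objective 2 groups differ in dose between surgery and the dCD test.

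The protocol's own theory makes that interval relevant. Sections 2.1 and 2.2 suggest that statins may take part in injury repair, and Section 2.1.5 cites protection in coronary intervention after as little as 3 days of dosing.

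At stake is the reading of one result. If Arm 1 shows less dCD, the wording of Objective 2 invites the conclusion that 2-18 doses are not enough, when later dosing could be the cause. The interpretation text in Section 9.1 carries no caveat on this. The planned adjustment covers risk factors out of balance at p < 0.10 and does not name post-operative statin dose.

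**Working it through.** **1. The plan's own figure.** Section 9.2 gives a minimum detectable effect for Objective 2 of a 65% reduction in eCD (225 vs 338, power 0.8, alpha 0.05). It does not state the eCD rates used, so the figure cannot be confirmed. Using the two-proportion formula with pooled null variance, two-sided:

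power = Φ[(d − 1.96·SE0)/SE1], where d = p1 − p2, SE0² = p̄(1 − p̄)(1/338 + 1/225) and SE1² = p1(1 − p1)/338 + p2(1 − p2)/225.

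Solving for 80% power with p2 = 0.35·p1 gives p1 = 9.0% and p2 = 3.1%. That is plausible beside the 11.0% eCD reported for asymptomatic statin users in Sections 2.1.5 and 2.1.6, at which power would be 88%. No power figure is given for dCD.

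**2. Which comparisons are exposed.**

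| Comparison | Randomised? | Own pre-study prescriptions | Exposed at Day 30? |
|---|---|---|---|
| Objective 1 (Arm 2, 338 vs 337) | Yes, blinded | Sub-maximal in both | No systematic difference expected |
| Objective 2 (Arm 1 225 vs raised Arm 2 338) | No | Maximal vs sub-maximal | Yes |
| Objective 3 (Arm 3, 50 vs 50) | Yes, blinded | No statin in both | No systematic difference expected |
| Objective 4 (pooled by dose at surgery) | Mixed | Mixed | Only through Arm 1 |

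eCD is measured 12-25 h after surgery, too early for later prescribing to matter much in any row.

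**3. Arm 1 share in Objective 4.** Arm 1 plus raised Arm 2 is 225 + 338 = 563, and 225/563 = 40%. Adding the 50 Arm 3 patients on atorvastatin 80 mg gives 613, and 225/613 = 37%.

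**4. What post-operative dosing alone could produce.** Assume no pre-operative difference at all, and that post-operative dosing gives Arm 1 a Day 30 risk ratio r against raised Arm 2. Both r and the comparator dCD rate (5-16%) are assumptions. The value r = 0.533 is 1 − 0.467, borrowed from the Arm 2 detectable effect. The opposite tail is added to the formula above.

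Example with comparator 11% and r = 0.75: p2 = 8.25%, p̄ = 9.90%, SE0 = 0.0257, SE1 = 0.0250. Then (0.0275 − 1.96 × 0.0257)/0.0250 = −0.91, and the chance of significance is 18%.

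For Objective 4 the diluted ratio is (225r + 338)/563, compared with 337 patients left at sub-maximal dose.

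| r | Objective 2: chance of p < 0.05 | Objective 4: diluted ratio | Objective 4: chance of p < 0.05 |
|---|---|---|---|
| 1 | 5% | 1 | 5% |
| 0.90 | 6-8% | 0.96 | 5-6% |
| 0.75 | 10-26% | 0.90 | 7-10% |
| 0.533 | 27-75% | 0.81 | 11-24% |

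Ranges run over comparator rates of 5% to 16%. Including Arm 3 (613 vs 337 + 50 = 387) lowers the Objective 4 figures slightly.

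**The case against.** **The dose difference is an inference.** A reader might infer that Arm 1 stays on maximal dose and that supplemented patients revert. The documents do not say so. Arm 1's continuation is stated only for the pre-operative period, and Section 3 and Appendix V leave everyone to standard of care, which could narrow the gap. This stands: the difference is likely, but neither fixed nor of known size.

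**Day 30 is not only about later dosing.** The proposed mechanism is hypoperfusion during surgery (Section 2.1.1), so dCD also captures lasting peri-operative injury. A pre-operative regimen followed by usual care, analysed by intention to treat, is a legitimate question. This stands too: the contrast is confounded, but not empty.

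**Equal dCD would still say something.** A reader might conclude that the dCD comparison fails whichever way it turns out. If Arm 1 does stay maximal and that helps, the bias runs against supplementation, and similar rates would lean towards sufficiency. The lean is slight, because the groups are not randomised and the detectable effect for eCD is as large as 65%.

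**Objective 4 is not affected to the same degree.** Raised Arm 2 patients stopping study drug is not confounding, since the same happens in Objective 1. Only the Arm 1 share introduces a between-group difference, and Objective 4 does not ask about sufficiency of the short course.

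**Much of the remedy is already there.** eCD is already the primary response. But Objective 2 still names dCD as a basis for judging sufficiency, and nothing in the plan limits that reading.

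**Conclusion.** The point holds for the dCD part of Objective 2. Lower dCD in Arm 1 could not be attributed to the 2-18 dose course being too short. It holds in diluted form for Objective 4, through the 37-40% of the pooled maximal group that comes from Arm 1. eCD and the dCD analyses of Objectives 1 and 3 are essentially unaffected.

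The conclusion rests on one unstated but likely premise, that post-operative prescriptions largely follow the pre-study ones. It also supposes that dose in that interval can affect Day 30 performance. The bias cannot be sized from the documents. Comparing the length of the post-operative interval with the number of pre-operative doses would not size it either, and the clinic-visit alternative to Day 30 has no stated limits. The simulated-scenario percentages above illustrate sensitivity to assumed values and are not estimates.

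This is a cheap improvement to what may be concluded. It is not a flaw in the trial's primary analysis.

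**What to change.** 1. In Objective 2, rest any conclusion about the sufficiency of the pre-operative course on eCD.
2. Describe the dCD contrast in Objective 2 as pre-operative plus usual post-operative regimen. Add the same description as a caveat to the dCD part of Objective 4.
3. Tabulate statin and dose from CEA to Day 30 by group, using the Concomitant Medications eCRF. This shows whether the presumed difference occurred.
4. Do not offer dCD among patients at maximal dose on Day 30 as evidence. That subgroup is selected on post-operative prescribing, which can itself respond to CK or LFT results (Section 7.2.1). If prescriptions simply carry on, it would contain no supplemented Arm 2 patients.
5. Leave dCD as planned for Objectives 1 and 3.

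The cost is some rewording and one table from data already collected, with no change to treatment or visits. The downside is a weaker dCD claim for Objective 2.

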4 SELECTION AND ENROLLMENT OF PARTICIPANTS

The subject participants must meet all of the inclusion criteria and not meet any exclusion criteria in order to be enrolled and assigned to an arm of this study.

4.1 Inclusion Criteria

- 1) Age ≥ 18 years of age.
- 2) Patient is currently on atorvastatin or simvastatin or rosuvastatin or statin naïve (no statins in the last 30 days).
- 3) The patient has unilateral or bilateral carotid artery stenosis that is considered severe (carotid artery diameter reduction $\geq 70\%$) as defined by any of these: a) Peak systolic velocity of at least 230 cm/s OR
b) CTA showing $\geq 70\%$ stenosis OR
c) MRA showing $\geq 70\%$ stenosis
- 4) The patient's attending doctor(s) (PMD, cardiologist, vascular/neurosurgeon) AND the patient have decided to proceed with a CEA to treat the patient's severe carotid stenosis.
- 5) The patient has no known circumstance or condition likely to preclude 1 year follow-up or adherence to the study protocol.
- 6) The patient is independent in their Activities of Daily Living at baseline (without cognitive, hearing or visual impairments which would impede NP testing). Walking impairments will not be a reason for exclusion.
- 7) Patient has the ability to provide informed consent.

4.2 Exclusion Criteria

- 1) Patient has underlying disease other than atherosclerosis (i.e. autoimmune disease, known active malignancy).

- 2) Patient has documented dementia or screens out based on abnormal Baseline MoCA (≤ 25) and AD8 (≥ 2).
- 3) Patient's life expectancy is < 12 months.
- 4) Patient has advanced renal failure (serum creatinine > 2.5 mg/dL)
- 5) Patient has evidence of severe congestive heart failure or has history of end-stage cardiovascular disease (e.g. CHF NYHA Class III or IV or unstable angina).
- 6) Patient has history of intolerance or allergic reaction to any statins (myotoxicity, hepatic dysfunction, rash, etc.) – unless they would be in the Observational Arm (Arm 1) and therefore will not be receiving any study drug.
- 7) Patient has received an investigational drug within 30 days.
- 8) Patient is pregnant or lactating.
- 9) Except those eligible for the Observational Arm who do not receive any study statin, patient who is currently taking any of the following which have been shown to interact with atorvastatin and/or simvastatin and/or rosuvastatin (as per current drug package inserts):
 - *Cyclosporine;
 - *HIV Protease Inhibitors/Antivirals (e.g. roatanavir or plus roatanavir, tipranavir, lopinavir, boceprevir, saquinavir, darunavir, fosamprenavir, nelfinavir, efavirenz/tenofobir, atazanavir, simeprevir);
 - *Hep C Protease Inhibitor/Antivirals (e.g. telaprevir);
 - *Antibiotics (i.e. cobicistat-containing products like Tybost, rifampin/rifampicin, clarithromycin, telithromycin, erythromycin);
 - *Anti-fungals (i.e. itraconazole, ketoconazole, posaconazole, voriconazole, fluconazole); *Gemfibrozil; Other Fenofibrates (e.g. Tricor, fibric acid);
 - *Niacin > 1 g/day or statins in combination with niacin (e.g. Vytorin, Simcor);
 - *Colchicine;
 - *Danazol;
 - *Calcium Channel Blockers: Diltiazem, Varapamil;
 - * Dronedarone;
 - *Amiodarone;
 - *Digoxin;
 - *Ranolazine;
 - *Nefazodone;
 - *Warfarin/Coumadin;
 - *Lomitapide;
 - *Grapefruit juice (subject must be willing to avoid grapefruit juice).

